Protocol Title:

Educating Women about Pelvic Floor Disorders during Pregnancy From the 1st to the “4th trimester”

Principal Investigator:

[name] FPMRS, Houston Methodist Hospital, Houston, TX

Co-Investigators:

[name] MD FPMRS, Houston Methodist Hospital, Houston, TX

[name] MD FPMRS, Houston Methodist Hospital, Houston, TX

[name] PhD, University of Houston, Houston, TX

SPONSOR / FUNDING AGENCY

None

VERSION NUMBER/DATE

Version 8 10/8/20

REVISION HISTORY

Revision #	Version Date	Summary of Changes	Consent Change (Yes/No)
1	7/1/20	Addition of virtual version of workshops	Yes
2	10/8/20	Addition of postpartum phone follow up	No

1. Study Summary

Pelvic floor disorders (PFDs) are common and significantly affect the quality of life of many women as they age. Pregnancy has been identified as a major risk factor for developing PFDs later in life. Educating women about PFDs is essential to ensuring that they present to care in a timely manner. No study has investigated different education tools during pregnancy. The proposed study is a randomized controlled trial in pregnant patients comparing two educational tools: written materials about PFDs versus an educational workshops led by pelvic floor physical therapists (PFPTs). Pregnant patients will be recruited in the first and second trimester and randomized at that time. Knowledge will be assessed at baseline and again 6 weeks postpartum using the validated Prolapse and Incontinence Knowledge Questionnaire. Secondary outcomes will be evaluating referral patterns to urogynecology and to PFPTs from general OBGYNs and assessing any pelvic floor symptoms with the pelvic floor disability index (PFDI-20) at baseline and at 6 weeks postpartum.

2. Purpose of the Study / Objectives

Hypothesis: Patients attending an educational workshop from pelvic floor physical therapist (PFPT) on pelvic floor anatomy, physiology, and disorders will have improved knowledge of pelvic floor disorders (PFDs) as measured by the Prolapse and Incontinence Knowledge Questionnaire (PIKQ) than those in the written education group.

Primary aim:

To determine the change in knowledge regarding PFDs as measured by the PIKQ in pregnant patients attending education compared to written education alone.

Secondary aims:

To determine whether pregnant patients receiving written education or attending an educational workshop on PFDs increases referral rates to either PFPT or urogynecology.

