The obstetrics practice that we will be recruiting from has approximately 75 obstetrics patients per month. Assuming approximately 50% recruitment each month, we anticipate being able to complete recruitment in 6 months. We will start educational workshops once 10 patients are enrolled into the educational workshop arm of the study. In order to offer adequate availability to patients, we will plan to offer four workshops per month. As scheduling the workshops may pose a logistical challenge, we will assess patient availability and adjust timing of the workshops to maximize the number of patients at each workshop. We will continue to follow these patients through their pregnancy so the timeline of data collection will continue for approximately 9 months after the recruitment period ends. We estimate that data collection will be completed by August 2021.

2020			
July			
Aug			
Sept			
Oct			
Nov			
Dec			
2021			
Jan			
Feb			
Mar			
Apr			
May			
June			
July			
Aug			

Recruitment period

Educational workshops
four times per month

Data collection period will
continue until 3 months after the
completion of the intervention to
capture both questionnaire and
referral pattern data.

Inclusion criteria:

- Patients in the first or second trimester of pregnancy
- English speaking
- Greater than 18 years old

Exclusion criteria:

- Non-English speaking or unable to provide informed consent

5. Study Intervention

At the first research visit, patients will be consented and randomized. Patients may be approached regarding the study by phone. The research consent form will be sent to them via e-mail for them to review and they will sign the consent at their next in-person visit. They will complete the PIKQ and PFDI-20 questionnaires (Appendix A).^{8,9} After their baseline questionnaires are completed, they will receive written educational materials.

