6. Drugs, Biologics, Devices

No drugs, biologics, or devices will be used for this study.

7. Collaborative / Multi-site Research

This study will take place at one site within the Methodist system.

8. Data Privacy / Confidentiality

Houston Methodist policies for Protected Health Information (PHI) will be followed in access patient charts. PHI will be used to identify patients that are eligible for the study by reviewing clinical schedules. Patients will be assigned a subject ID number that is deidentified. There will be a master data sheet that will have patient MRNs associated with their subject ID number that is separate from the RedCap database. This data sheet will be stored on an encrypted password protected USB drive. No PHI will be disclosed. The data will be maintained for 6 years after the completion of the study and then destroyed.

The web based virtual workshop will not include the patient's personal information, including their name, unless they want to provide their name. They have the option to share their video or participate verbally in the workshop but it is not required. All participants will be muted and their video off on entry to the virtual meeting and they can choose to disable these features if desired. The virtual workshop meeting room will be password protected. This password will be provided to the participants via e-mail the day of the workshop. There will be a phone number to a study team member provided to them to call for any technical support if needed. None of the sessions will be recorded.

Identifier (or parts of)	Recorded	Disclosed	Comment
All elements of dates (except year) for dates directly related to an individual, including birth date, admission date, discharge date, date of death; and all ages over 89 and elements of dates (including year) indicative of such age	X		
Medical record numbers	X		
Phone number			Used for recruiting patients after virtual visits with their doctor.
Email address			Used to send questionnaires and consent forms if recruited virtually. Used to send password for virtual workshop.

9. Data and Specimen Banking

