There are minimal risks associated with this study. The cost of parking in the medical center may pose a burden to some subjects and so we plan to compensate the cost of parking to try to offset this. Otherwise, there is no physical, social, legal, or psychological risk to the subjects.

15. Potential Benefits

Regardless of the group to which the subjects are randomized, they will be given education on PFDs that they would not typically receive in their routine obstetric care. This may provide the opportunity to make subjects aware of treatment options for PFDs that they were not aware of and provide them an opportunity to improve their quality of life.

A potential challenge would be ensuring that patients receive their follow up assessment as patients may not show up for their postpartum visit. A strategy to improve follow up would be to consent patients to the option of receiving and completing the PIKQ and PFDI-20 by e-mail if they do not attend their postpartum visit. Another potential challenge may be ensuring that patients attend their assigned group workshop. A strategy to improve attendance and

enrollment would be to compensate patients. We plan to compensate their parking on the dates that they attend the group workshop.

16. Financial and Economic Issues

The only cost to the study subjects will be the cost of parking to attend the group workshop. The remainder of the study visits will occur at the same time as routine care visits. We will plan to compensate the cost of parking at the time of their group workshop with an estimated cost of \$960 (\$16 per participant).

17. Data Safety Plan

Please see above description of Data and Specimen Banking.

18. Informed Consent Documentation and Process

Informed consent will be obtained prior to any of the study procedures with the attached informed consent template. Consent will be obtained from a member of the research team. The consent document may be e-mailed to participants after being recruited by phone for their review. They will then sign the consent form at their next in-person physician visit.

19. Waiver of Informed Consent and /or Authorization

A screening waiver will be requested preparatory for research (waiver requested for feasibility, recruiting, access to charts, pre-screening). We are not requesting a waiver of informed consent.

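### Section 5 lists randomisation before the baseline PIKQ and PFDI-20 and does not require the baseline to be finished before the arm is revealed

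*Combined protocol and SAP*

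**What the plan says.** The steps at entry are described in Section 5 (Study Intervention). The opening sentence is "At the first research visit, patients will be consented and randomized". The paragraph then turns to the approach by phone and the e-mailed consent form, and says of these women that "they will sign the consent at their next in-person visit". Next it lists the two baseline questionnaires, and it closes with "After their baseline questionnaires are completed, they will receive written educational materials".

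Section 1 (Study Summary) ties randomisation to recruitment: "Pregnant patients will be recruited in the first and second trimester and randomized at that time". It mentions the baseline knowledge assessment in the following sentence.

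Two other places bear on the order. Section 18 states "Informed consent will be obtained prior to any of the study procedures", which puts consent first but does not rank randomisation against the questionnaires. The identifier table in Section 8 gives the purpose of the e-mail address as "Used to send questionnaires and consent forms if recruited virtually", without saying whether those questionnaires go out before or after assignment.

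The primary aim in Section 2 is "To determine the change in knowledge regarding PFDs as measured by the PIKQ". Under Statistical Analysis in Section 4, the groups are compared by a t-test or Mann-Whitney test on each woman's paired difference. No baseline-adjusted model is given.

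**The concern.** Read in the order written, the steps are consent, randomisation, baseline forms, handouts. The authors protected the baseline from the teaching material but wrote no matching protection from knowledge of the arm. The documents describe no allocation concealment, no blinding and no rule on when the arm is disclosed. A woman will also know whether she is to attend a workshop.

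A woman who knows her arm may put more or less effort into a knowledge quiz, use the don't-know option differently, or look answers up, particularly if the form reaches her by e-mail. The PFDI-20 is a self-report of symptom bother and is at least as open to influence. If such behaviour differs by arm, the baseline scores differ for a reason other than chance. The primary comparison subtracts that baseline, so the difference would appear as part of the treatment effect.

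**Working it through.** **Order of steps.** The documents fix only two orderings: consent before any study procedure (Section 18) and baseline questionnaires before handouts (Section 5). Randomisation is named ahead of the questionnaires in both Section 1 and Section 5, but no sentence places it before or after them. Nor does any sentence require the baseline to be complete before the arm is revealed.

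**Inputs from Section 4.** PIKQ composite of 24 points; expected score 0.45 at baseline in both groups; 0.80 (workshop) and 0.54 (written) at follow-up; two-sided alpha 0.05; power 80%; 96 evaluable; 120 enrolled after 20% dropout.

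**The plan's own figure.** The unpooled normal formula for two proportions reproduces it:

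n per arm = (1.960 + 0.842)² × (0.54 × 0.46 + 0.80 × 0.20) / 0.26² = 7.849 × 0.4084 / 0.0676 = 47.4, rounded up to 48.

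That gives 96 in total, and 96 / 0.80 = 120. (The pooled variant named in the text gives 51 per arm, or 102; that is a separate matter.) The order of baseline and randomisation is not an input, so the sample size is unaffected by this point. I use 48 per arm below.

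**Planned difference in change.** (0.80 − 0.45) − (0.54 − 0.45) = 0.35 − 0.09 = 0.26, or 0.26 × 24 = 6.2 points.

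**How a baseline shift carries over.** The contrast is D = (F_W − B_W) − (F_H − B_H), where F is follow-up, B is baseline, W is workshop and H is written education. If knowing the arm moves B_W by s relative to B_H, and follow-up is unaffected, D moves by −s. The full amount passes through, with the sign reversed.

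- Half an item: 0.5 / 24 = 0.021, or 8% of 0.26.
- One item: 1 / 24 = 0.042, or 16% of 0.26.
- Two items: 2 / 24 = 0.083, or 32% of 0.26.

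**False-positive rate, for illustration.** The documents give neither an SD of change nor a size for any shift, so both are my assumptions. With no true effect, SE = SD × √(2/48), and the rejection probability is Φ(s/SE − 1.96) + Φ(−s/SE − 1.96). For one item and SD 0.20, SE = 0.0408 and s/SE = 1.02, which gives 17.5%.

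| Assumed SD of change | Half-item shift | One-item shift |
|---|---|---|
| 0.15 | 10.4% | 27.5% |
| 0.20 | 8.0% | 17.5% |
| 0.25 | 6.9% | 12.9% |

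**Would baseline adjustment remove it?** Only in part. With ANCOVA, the slope times the shift carries over. For one item and assumed slopes of 0.3 to 0.7, that is 0.013 to 0.029 instead of 0.042.

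**The case against.** The strongest reply is that this is loose drafting and no more. The Section 5 paragraph is not chronological: it names consent and randomisation first, then goes back to the phone approach and the signing of consent, which must come earlier. Sentence order therefore cannot establish step order. Randomising a woman is also not the same as telling her the result. This stands. A reader might infer that women are in fact randomised and told their arm before the baseline; the documents do not support that. They support only that randomisation is listed first and that nothing prevents it.

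Second, no study teaching can reach the baseline score. The handouts explicitly follow the questionnaires, and the workshop follows randomisation. This also stands. What remains is effort, guessing or looking up answers, and for bias these must differ on average between arms. The documents give no evidence that they would.

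Third, the shifts considered are small against a planned difference of 6.2 points. A one-item shift could not create an effect of that size; it would move an estimate of 0.26 to about 0.22 or 0.30. That is correct, and it limits the importance of the point.

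A reader might also infer that women disappointed with their arm would leave before giving a baseline, so that missing data differ by arm. For clinic recruits the text points the other way. Section 5 gives the written group its handouts at the first study visit, and the handouts come after the forms, so allocation and baseline appear to fall on one visit. Such loss is more conceivable among women sent forms by e-mail, but the timing of those forms is not stated.

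None of this supplies the missing rule. If staff already collect the baseline first, the protocol does not show it.

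**Conclusion.** The point holds as a gap in the plan and does not show that bias has occurred. Section 5 lists randomisation ahead of the baseline questionnaires and leaves open that they are answered with the arm known, in a trial whose participants cannot be blinded and whose primary test subtracts that baseline in full.

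Any arm-related shift would pass one for one into the primary comparison, at 0.042 per item. Its size and direction are unknown. The rates of about 13–28% for a one-item shift should not be read as this trial's error rate. They assume no true effect, 48 per arm, an SD of change between 0.15 and 0.25, and that the whole shift occurs. This is a cheap improvement, not a fatal defect.

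**What to change.** Reorder Section 5 so that the sequence is explicit:

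1. Obtain signed consent.
2. Have the woman complete the baseline PIKQ and PFDI-20, and lock both, including any sent by e-mail.
3. Randomise, then disclose the arm.
4. Give the handouts.

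Align the Section 1 sentence on randomisation with this order.

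For clinic recruits the visit, staff and forms do not change. For women recruited by phone or e-mail, allocation waits until their forms are received, which is the one small cost. The sample size stays at 96 evaluable and 120 enrolled. Version 8 is dated 10/8/20 and the timeline in Section 4 starts in July 2020, so recruitment may already have begun. If so, the new order applies to women enrolled from then on, and the report should say that the procedure changed.

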Patients' baseline characteristics will be summarized according to the two groups. All data will be presented as mean \pm SD or median (interquartile range) for continuous variables, and number (percentage) for categorical variables. Chi-squared or Fisher's exact test (categorical variables) and Student's t-test or Mann-Whitney test (continuous variables) will be used to compare patients between PFPT and written education group at baseline. Paired t-test or Wilcoxon signed-rank test will be used to compare questionnaire scores between baseline and the follow-ups within each group. Student's t-test or Mann-Whitney test will be used to compare the paired difference between the two groups. The Shapiro-Wilk test will be used to check the normality. Pearson's correlation coefficient or Spearman's rank correlation coefficient will be used to analyze the relationships among variables. All analyses will be performed with STATA version 16 (StataCorp. 2019. Stata Statistical Software: Release 16. College Station, TX: StataCorp LLC). Statistical significance will be defined as two-tailed $p < 0.05$ for all tests.

Sample Size Calculation:

Our primary objective of the proposed study is to evaluate the hypothesis that patients attending an educational workshop from PFPTs will have improved knowledge of pelvic floor disorders (PFDs) as measured by the Prolapse and Incontinence Knowledge Questionnaire (PIKQ) as compared to patients in the written education group. We will use the 24-point PIKQ questionnaire composite score as our primary endpoint. Based on the PIKQ validation study, a composite score of 0.45 (45%) is expected in women of this age at baseline.⁸ Assuming in our study population at baseline a score of 0.45, we would expect an increase in the composite

score to 0.8 in the PFPT group and an increase in composite score to 0.54 in the written education group. Therefore, a sample size of 96 patients will be needed to detect the difference with 80% power and a significance level of 0.05 based on the two-sided Z-test with pooled variance. After considering 20% dropout rate from the study, the total sample size will be 120 patients (60 per group). PASS 2015 (PASS 15 Power Analysis and Sample Size Software (2017). NCSS, LLC. Kaysville, Utah, USA, ncss.com/software/pass) was used for sample size calculation.

Study Timeline:

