Patients randomized into the written education group will only receive written materials. They will receive these materials at the first study visit and again when leaving the hospital after delivery. The written materials will consist of three one-page handouts with information on pelvic organ prolapse (POP), stress urinary incontinence (SUI), and pelvic floor exercises. These handouts will be created in collaboration with [name] and [name] who have experience in the study of patient's perceptions of PFDs and have collaborated with the American Urogynecology Society to create written educational materials in the past.⁴ We plan to seek feedback from patients regarding their impressions of our newly developed handouts prior to use.

The PFPT workshop group will both receive the written handouts and attend an in-person education workshop that will be led by a PFPT with approximately 5-10 study participants in each workshop. Patients will be allowed to attend the workshop after being randomized during pregnancy or during the postpartum period to maximize participation. The session will last approximately 1 hour and will review similar information to the content of the handouts. It will focus on educating the patients about pelvic floor anatomy, etiology of PFDs, prevention strategies, and informing them about urogynecologists and PFPTs. The educational workshops will be offered in either in person or virtual format to accommodate group gathering restrictions of COVID-19. The web-based meeting will be password protected and participants will have the option to share their video and do not have to provide their name as the participant if they do not want to. They have the option to verbally participate but this is not required.

Patients will be reassessed and complete the PIKQ and PFDI-20 questionnaires at their 6-week postpartum visit. We will also record delivery type. If patients do not attend their postpartum visit, they will be reached by phone or e-mail to complete the postpartum assessment. Referral patterns to PFPT and urogynecology will be assessed using electronic medical records during the study period and up to 3 months postpartum.

Patients from the workshop group will receive a follow up phone call to perform a brief phone survey on their perceptions of the two forms of educational materials: written versus workshop format. No medical information will be discussed in this phone call. Please see interview guide attached in appendix ***.

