Patient demographic data will be collected from the medical record and the PIKQ survey, including age, race, obstetrics history, marital status, household income, and education level. Delivery type will also be recorded at the 6 weeks postpartum visit. The patients will be asked to give responses to the PIKQ and PFDI-20 surveys. Data collected in the study will include referral patterns within the OBGYN group at Methodist to the urogynecology group and pelvic floor physical therapy group. The referral information will be collected for the 6 months

preceding the study and compared to the data collected during the study period. This data will be recorded on recruitment paperwork with a de-identified subject ID and recorded into a RedCap database.

10. Study Population

We will recruit female patients in the first or second trimester of pregnancy who are 18 years of age or older.

11. Screening and Recruitment^{SR}

Patients will be identified by reviewing the clinical schedule of the general obstetrics providers at Houston Methodist Hospital. The patients will be approached either in the waiting room prior to their appointment or while they are awaiting their physician visit in the clinic room. Patients may also be approached by phone after their visit with a physician if they are attending virtual visits. Recruitment flyers will be posted around the clinical area and waiting room of the Smith 2221 OBGYN clinical area.

12. Withdrawal of Subjects

Subjects may withdraw from the study at any time with no change to their routine obstetric care. Patients who experience a miscarriage or intrauterine fetal demise prior to viability will be withdrawn from participation.

13. Provisions to Protect the Privacy Interests of Subjects

Subjects will be required to provide minimal demographic information at their recruiting visit and this will not need to be repeated at any point. Their primary interaction with the research study team will be at recruitment, at the PFPT group workshop, and at their postpartum visit for the follow up questionnaire administration. The educational workshop will include females only and female PFPTs in small groups of 5-10 subjects. We plan to offer the workshops in either an in-person or virtual format to accommodate for current group gathering constraints due to COVID-19.

14. Risks to Subjects

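### Only the workshop arm is taught in shared sessions, yet the primary test treats all women as independent; if knowledge is correlated within sessions, the standard error is too small

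*Combined protocol and SAP*

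**What the plan says.** Women are randomised individually to two arms. Section 5 (Study Intervention) gives both arms the handouts and adds, for one arm, a session of about an hour "led by a PFPT with approximately 5-10 study participants in each workshop". Section 13 repeats the format: "female PFPTs in small groups of 5-10 subjects". Sessions may be in person or virtual and may be attended during pregnancy or postpartum. The written arm has no group element.

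For the between-group comparison, Section 4 (Statistical Analysis) states: "Student's t-test or Mann-Whitney test will be used to compare the paired difference between the two groups". The Sample Size Calculation in the same section says "a sample size of 96 patients will be needed to detect the difference with 80% power", with "a significance level of 0.05 based on the two-sided Z-test with pooled variance", and then inflates to 120 for 20% dropout. The documents give no ICC, design effect, session or therapist term, or cluster-robust standard error. The data items listed in Section 9 do not include the session attended or the therapist.

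**The concern.** Women in the same session share a therapist, a format, a date and whatever discussion takes place. Their later scores on the knowledge questionnaire (PIKQ) may therefore resemble each other more than those of women taught separately. Randomisation is individual but delivery is grouped in one arm only, so the design is partially nested. The t-test and the Mann-Whitney test both assume independent observations within each arm. If scores are positively correlated within sessions, the variance of the workshop-arm mean is larger than the test supposes. The primary comparison then rejects too often under the null hypothesis, and its confidence interval is too narrow.

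**Working it through.** **Inputs from Section 4.** Two-sided alpha 0.05; 80% power; 96 evaluable women (48 per arm); expected scores 0.80 (workshop) and 0.54 (written); 20% dropout.

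**Inputs from Sections 5 and 13.** Session size m of about 5 to 10, workshop arm only.

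**Assumed.** ICC of 0.01, 0.05 and 0.10, because the documents give none.

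**Step 1: the plan's own figure.** Treating the scores as proportions, with unpooled variance:

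n per arm = (1.96 + 0.8416)² × (0.80×0.20 + 0.54×0.46) / 0.26² = 7.849 × 0.4084 / 0.0676 = 47.4, so 48 per arm and 96 in total. Then 96 / 0.8 = 120.

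The stated size is reproduced. (The pooled formula that the plan names gives 51 per arm, or 102; that is a separate point.) The only inflation is for dropout.

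**Step 2: effect of session clustering on the planned test.** With equal arms and clustering in one arm:

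- Design effect in the workshop arm: DE = 1 + (m − 1) × ICC
- True SE / SE used by the test: r = √((1 + DE)/2)
- True type I error = 2 × (1 − Φ(1.96/r))

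For example, m = 10 and ICC = 0.10 give DE = 1.90, r = √1.45 = 1.204, and 2 × (1 − Φ(1.628)) = 10.4%.

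| m | ICC | DE | r | True type I error |
|---|---|---|---|---|
| 5 | 0.01 | 1.04 | 1.010 | 5.2% |
| 5 | 0.05 | 1.20 | 1.049 | 6.2% |
| 5 | 0.10 | 1.40 | 1.095 | 7.4% |
| 10 | 0.01 | 1.09 | 1.022 | 5.5% |
| 10 | 0.05 | 1.45 | 1.107 | 7.7% |
| 10 | 0.10 | 1.90 | 1.204 | 10.4% |

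Simulating the planned t-test (50 per arm, 40,000 replicates per scenario) gave similar rates. For 10 sessions of 5 and 5 sessions of 10 respectively, they were 6.4% and 7.6% at ICC 0.05, 7.1% and 10.5% at ICC 0.10, and about 5% for both at ICC 0.

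**Step 3: smaller sessions.** Section 4 (Study Timeline) plans four workshops a month and six months of recruitment. If all of them run over those six months, there are 24 sessions for 60 women, or 60/24 = 2.5 each. Type I error is then 5.4% at ICC 0.05 (DE 1.075) and 5.9% at ICC 0.10 (DE 1.15).

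**Step 4: power.** Two quantities must be kept apart. Starting from a nominal 80% (1.96 + 0.8416 = 2.8016):

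- A valid, cluster-adjusted test has power Φ(2.8016/r − 1.96).
- The planned, unadjusted test rejects with probability Φ((2.8016 − 1.96)/r).

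| m | ICC | Adjusted test | Planned test |
|---|---|---|---|
| 5 | 0.05 | 76% | 79% |
| 10 | 0.05 | 72% | 78% |
| 5 | 0.10 | 72% | 78% |
| 10 | 0.10 | 64% | 76% |

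The adjusted figures are before any small-sample degrees-of-freedom penalty.

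**Step 5: would the planned effect survive?** Treat the score as a mean with difference 0.26, 48 per arm, m = 10 and ICC 0.10. With an assumed SD of 0.30, SE = 0.30 × √(2.90/48) = 0.0737, and adjusted power is Φ(0.26/0.0737 − 1.96) = 94%. With SD 0.20 it is above 99%. With SD 0.40 it would be 75%.

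**Step 6: p-values.** A naive p of 0.05 corresponds to 0.062 (m = 5) to 0.077 (m = 10) at ICC 0.05, and to 0.074 to 0.104 at ICC 0.10. A naive p of 0.001 corresponds to at most 0.006 over the same four cases.

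**The case against.** The strongest reply is that the ICC may be close to zero. The session lasts about an hour and covers much the same ground as handouts that both arms receive. Virtual attendees enter muted with video off and need not speak. The outcome is measured at 6 weeks postpartum, possibly months after an antenatal session. A shared therapist creates correlation within sessions only if therapists differ between sessions, and their number is not stated. Sessions may also be smaller than 5 to 10, and women who attend none add no session clustering. All of this stands as a reason to state the point conditionally. It does not show that the ICC is zero. The plan twice gives 5 to 10 per session, and the Study Timeline says scheduling will be adjusted to fill them.

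A reader might infer that the planned test combines a type I error of up to 10% with power as low as 64%. It does not: the first belongs to the unadjusted test and the second to a cluster-adjusted test held at 5%. The 80% starting value is itself doubtful, because it comes from treating a mean score as a proportion.

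A reader might also assume that attendance records will already show who sat in which session. The documents describe no such records, virtual participants need not give their names, and sessions are not recorded (Sections 5 and 8).

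**Conclusion.** The concern holds conditionally. The design is grouped in one arm, the test assumes independence, and nothing in the plan allows for the grouping. Over assumed ICCs of 0.01 to 0.10, the true type I error of the planned test runs from 5.2% to 7.4% with 5 per session and from 5.5% to 10.4% with 10. It is below 6% in this ICC range if sessions average about 2.5 women.

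It would go too far to say that the standard error is certainly too small, or that clustering threatens the main conclusion. The first needs an ICC above zero, which the documents neither give nor exclude. On the second, if the 0.54 versus 0.80 difference is real and the SD is 0.20 to 0.30, an adjusted test would still have at least 94% power in the worst case tabulated. What is at risk is the width of the interval, and the p-value if the observed effect is smaller than planned.

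**What to change.** Add a data field that links each subject ID to the session attended and the therapist, with a procedure that also works for virtual sessions where names are optional. This must be collected as sessions happen, since the link may not be recoverable later.

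Prespecify a partially nested model for PIKQ: a random session effect in the workshop arm only, written-arm women and workshop-arm non-attenders as singletons, and small-sample degrees of freedom. Report the estimated ICC. In the sample size section, state power with an assumed ICC and the resulting design effect.

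The cost is one new field and a paragraph of analysis text, a wider interval and a lower stated power. With only about 6 to 12 sessions implied (60/10 to 60/5), the session variance will be estimated imprecisely, and the plan should say so.
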